APPENDIX 2: ECOG PERFORMANCE STATUS

ECOG PERFORMANCE STATUS*	
Grade	ECOG
0	Fully active, able to carry on all pre-disease performance without restriction
1	Restricted in physically strenuous activity but ambulatory and able to carry out work of a light or sedentary nature, e.g., light house work, office work
2	Ambulatory and capable of all selfcare but unable to carry out any work activities. Up and about more than 50% of waking hours
3	Capable of only limited selfcare, confined to bed or chair more than 50% of waking hours
4	Completely disabled. Cannot carry on any selfcare. Totally confined to bed or chair
5	Dead

*Oken et al, 1982

APPENDIX 3: RESPONSE ASSESSMENT*

Response category	Definition
Complete response (CR)	
 • Absence of serum monoclonal IgM protein by immunofixation • Normal serum IgM level^a • Complete resolution of lymphadenopathy and splenomegaly if present at baseline • Morphologically normal bone marrow aspirate and trephine biopsy
Very Good Partial Response (VGPR)	
 • Detectable monoclonal IgM protein • $\geq 90\%$ reduction in serum IgM level from baseline^b • Complete resolution of extramedullary disease, i.e. lymphadenopathy/splenomegaly if present at baseline • No new signs or symptoms of active disease
Partial response (PR)	
 • Detectable monoclonal IgM protein • $\geq 50\%$ but $<90\%$ reduction in serum IgM level from baseline^b • Reduction in extramedullary disease, i.e. lymphadenopathy/splenomegaly if present at baseline • No new signs or symptoms of active disease
Minor response (MR)	
 • Detectable monoclonal IgM protein • $\geq 25\%$ but $<50\%$ reduction in serum IgM level from baseline^b • No new signs or symptoms of active disease
Stable disease (SD)	
 • Detectable monoclonal IgM protein • $<25\%$ reduction and $<25\%$ increase in serum IgM level from baseline^b • No progression in extramedullary disease, i.e. lymphadenopathy/splenomegaly • No new signs or symptoms of active disease
Progressive disease (PD)	
 • $\geq 25\%$ increase in serum IgM level^{a,b} from lowest nadir^c and/or • Progression in clinical features attributable to the disease

*Owen et al, 2013

^aIgM responses/progression should be confirmed by a second measurement (ideally taken within the same cycle as the initial measurement)

^bSequential changes in IgM levels may be determined either by IgM protein quantitation by densitometry or total serum IgM quantitation by nephelometry

^cThe effects of any plasmapheresis should be considered when determining the lowest nadir

Note: where local investigations are inconclusive in determining progression, or the Site are uncertain that the progression in clinical features is attributable to the disease, the TMG should be contacted for advice. In these circumstances please email [contact].

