1. PROTOCOL SUMMARY

1.1. Summary of Trial Design

Title:	A Phase II trial to investigate the safety and efficacy of rituximab and pembrolizumab in relapsed/refractory Waldenström's macroglobulinaemia
Short Title/acronym:	PembroWM
EUDRACT no:	2018-001767-23
Sponsor name & reference:	UCL18/0131
Funder name & reference:	Merck Sharp and Dohme Ltd; MISP# 56775
ISRCTN/Clinicaltrials.gov no:	NCT03630042
Design:	Single arm, phase II trial, non-randomised
Overall aim:	To determine the safety, tolerability and efficacy of pembrolizumab in combination with rituximab for the treatment of relapsed/refractory Waldenström's macroglobulinaemia (WM)
Primary endpoint:	Percentage of patients achieving an overall response rate (defined as complete response (CR), very good partial response (VGPR), partial response (PR) or minor response (MR) i.e. a greater than 25% reduction in the serum IgM level) at 24 weeks post commencing treatment.
Secondary endpoints:	
 Safety and tolerability of pembrolizumab in combination with rituximab Complete response (CR) rate at 24 weeks post commencing treatment Very good partial response (VGPR) rate at 24 weeks post commencing treatment Time to maximal response to treatment Time to next treatment Progression free survival (PFS) at 1 and 2 years Overall survival (OS) at 1 and 2 years Change in quality of life (QoL) at 24 weeks post commencing treatment
Exploratory Biological Studies:	
 Assessment of PD-1 and PD-L1/ PD-L2 expression by fluorescence in situ hybridisation (FISH) and immunohistochemistry (IHC)

[figure not shown]
	
 • IHC to assess baseline and on-treatment changes to distribution and composition of immune response cells in the microenvironment • Analysis of baseline biopsies to elucidate potential mechanisms of action of tumour response • Assessment of treatment outcome according to tumour genotype • Correlation of bone marrow response with reduction in serum IgM level • Quantification of bone marrow involvement by morphologic assessment of trephine and flow cytometric assessment of aspirate for MRD
Target accrual:	42 patients

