3.1. Trial Objectives

3.1.1. Primary Objective

- To determine the efficacy (overall response rate at 24 weeks) of the combination of rituximab and pembrolizumab in relapsed/refractory WM

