3.2. Trial Endpoints

3.2.1. Primary end-points:

- Percentage of patients achieving an overall response rate (defined as complete response (CR), very good partial response (VGPR), partial response (PR) or minor response (MR) i.e. a greater than 25% reduction in the serum IgM level) at 24 weeks post commencing treatment

3.2.2. Secondary end-points:

- Safety and tolerability of pembrolizumab and rituximab as assessed by the frequency of serious and non-serious adverse events, graded according to CTCAE v5.0
- Complete response (CR) rate at 24 weeks post commencing treatment (see appendix 4)
- Very good partial response (VGPR) rate at 24 weeks post commencing treatment (see appendix 4)
- Time to maximal response, as determined by the time of registration to the maximal disease response
- Time to next treatment, as determined by the time from registration to the next line of therapy
- Progression free survival (PFS) at 1 and 2 years
- Overall survival (OS) at 1 and 2 years
- Change in quality of life (QoL) at 24 weeks post commencing treatment

3.2.3. Exploratory endpoints:

- Assessment of PD-1 and PD-L1/ PD-L2 expression by fluorescence in situ hybridisation (FISH) and immunohistochemistry (IHC).
- IHC to assess baseline and on-treatment changes to distribution and composition of immune response cells in the microenvironment
- Analysis of baseline biopsies to elucidate potential mechanisms of action of tumour response
- Assessment of treatment outcome according to tumour genotype, as determined by sequencing assays for MYD88^{L265P} and CXCR4 mutations
- Correlation of bone marrow response with reduction in serum IgM level.
- Quantification of bone marrow involvement by morphologic assessment of trephine and flow cytometric assessment of aspirate for MRD

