6.2.1. Inclusion criteria

1. Patients ≥ 18 years old
2. Eastern Cooperative Oncology Group (ECOG) performance status 0-2 (see appendix 3)
3. Presence of measurable disease, (defined as a detectable level of IgM paraprotein) and fulfils other World Health Organisation (WHO) diagnostic criteria for WM
4. Relapsed or refractory WM who have received ≥ 1 prior lines of therapy
5. Adequate renal function: estimated creatinine clearance ≥ 30 ml/min as calculated using the Cockcroft-Gault equation
6. Adequate liver function, including:
 - o Bilirubin $\leq 1.5 \times$ the upper limit of normal (ULN)
 - o Aspartate or alanine transferase (AST or ALT) $\leq 2.5 \times$ ULN
7. Adequate organ and bone marrow function:
 - o Neutrophils $\geq 0.5 \times 10^9/L$
 - o Platelets $\geq 25 \times 10^9/L$

Note: Growth factor and/or transfusion support is permissible to stabilize participant prior to study treatment if needed. No lower limit if cytopenia is related to WM infiltration in the bone marrow.

8. Willing to comply with the contraceptive requirements of the trial (see section 6.3.4)
9. Negative serum or highly sensitive urine pregnancy test for women of childbearing potential (WOCBP)
10. Written informed consent

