8.3.3. Administration for IgM flare

Prior to the first cycle, if the total IgM is >40, pre-emptive plasmapheresis is recommended to get total IgM <40 and prevent IgM flare – defined as a >25% increase in total IgM. This phenomenon has been associated with single agent rituximab therapy in this setting, and can be associated with symptomatic hyperviscosity and/or escalation of WM related symptoms (e.g. neuropathy).

See section 8.4.6 for further details on IgM flare management.

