8.4.6. IgM flare

If there are any clinical or laboratory concerns about IgM flare in the first 2 cycles, plasmapheresis/other supportive care may be instituted and the subject may remain on trial treatment.

If at any timepoint after the end of cycle 2 plasmapheresis is required for symptomatic relief of IgM flare (or for any other reason), then the patient will have to cease study therapy and be managed as per standard of care at their institution.

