8.5. Treatment discontinuation

Trial treatment should be permanently discontinued if a patient experiences any of the following:

- disease progression whilst on trial
- an immune-related AE that does not resolve within 12 weeks of last dose of IMP
- treatment with corticosteroids cannot be reduced to ≤ 10 mg prednisolone or equivalent per day within 12 weeks
- Any grade 4 IMP related AE or laboratory abnormality apart from the following:
 - Grade 4 neutropenia <7 days (G-CSF may be instituted, and continued until neutrophils exceed $1.5 \times 10^9/L$, as per institutional policy)
 - Grade 4 lymphopenia
 - Grade 4 amylase abnormalities that are not associated with clinical symptoms
 - Grade 4 drug-related endocrinopathy AEs which are adequately controlled with physiologic hormone replacement
 - Electrolyte abnormalities that can be corrected and are not felt to be a cause for clinical safety concern.
- Grade 2 infusion related reaction (pembrolizumab related) for a second time despite receiving premedication
- Any grade 3 or 4 infusion related reaction (pembrolizumab related)

In instances where patients discontinue treatment, both pembrolizumab and rituximab should be discontinued. Patients will continue to be followed up in line with the protocol (see section 8.11).

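### The primary endpoint is counted both at and by 24 weeks, does not rank response against progression at week 24, and carries two definitions of response

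*Combined protocol and SAP*

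**What the plan says.** **Time point.** Section 1.1 counts "minor response (MR) i.e. a greater than 25% reduction in the serum IgM level) at 24 weeks post commencing treatment". The primary objective in section 3.1.1 is the "overall response rate at 24 weeks", and section 3.2.1 also says *at*. Sections 17.1 and 17.2.1 restate the same endpoint with *by*.

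**Definition of response.** Sections 1.1, 3.2.1, 17.1 and 17.2.1 list CR, VGPR, PR and MR and explain them by an IgM gloss, in section 3.2.1 "minor response (MR) i.e. a greater than 25% reduction in the serum IgM level". The opening of section 3 says response is assessed by serum IgM. Section 9.2.2 instead requires the working-group criteria. These are printed in Appendix 3, although sections 3.2.2 and 9.2.2 cite appendix 4, which is the version history. Appendix 3 sets MR at a fall of 25% or more and adds other conditions, such as "Reduction in extramedullary disease, i.e. lymphadenopathy/splenomegaly if present at baseline" for PR. VGPR, PR, MR and SD all require detectable monoclonal IgM.

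**Progression.** Appendix 3 measures PD as an IgM rise of at least 25% from the lowest nadir, or clinical progression. A footnote asks for confirmation by a second measurement. Section 8.5 lists "disease progression whilst on trial" as a reason to stop treatment. Section 8.3.3 describes flare, "defined as a >25% increase in total IgM", and section 8.4.6 says that in the first two cycles supportive measures "may be instituted and the subject may remain on trial treatment".

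**Missing data and success rule.** The table in section 17.2.1 applies only when the week-24 response is missing. Success is 23 or more responses in 42 patients.

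**The concern.** The trial has one arm and one pass/fail count. Two analysts following different sections could count different responders from the same data, and in an open-label trial the choice could be made after the results are known. The text as written even allows a patient in confirmed progression at week 24 to be counted as a responder.

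Appendix 3 read literally also orders some patients oddly. MR has no nodal condition, so a 30% IgM fall with unchanged nodes is MR. A 60% fall with unchanged nodes is not PR (no reduction in nodes), not MR (capped below 50%) and not SD.

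**Working it through.** **1. The plan's own figure.** Inputs from section 17.1: rates 40% and 60%, one-sided alpha 0.05, power 80%, n = 42, cut-off 23. With X binomial(42, p):

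- P(X ≥ 23 | 0.40) = 0.0375, within 0.05
- P(X ≥ 23 | 0.60) = 0.8032, above 0.80

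This is the smallest n that meets both conditions, so the design reproduces.

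**2. *At* against *by*, for a patient who responded at week 12.**

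| Week-24 result | *At* | *By* | Section 17.2.1 table |
|---|---|---|---|
| Observed SD | Non-responder | Responder | Silent |
| Observed PD only | Non-responder | Responder | Silent |
| Missing, alive, no progression reported | Needs a rule | Responder | Responder |
| Missing, progressed or died | Needs a rule | Responder | Non-responder |

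Under *by*, the third row needs no rule and the fourth contradicts the table. The table therefore fits *at*.

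**3. Response against progression.** Take no nodal disease, IgM 40 at baseline, 10 at nadir and a confirmed 15 at week 24.

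- From baseline: (15 - 40)/40 = -62.5%, which is PR
- From nadir: (15 - 10)/10 = +50%, which is PD
- Earlier fall: (10 - 40)/40 = -75%, so a responder under *by*

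Nothing says which category wins at week 24. The open case is narrow. Patients who progressed earlier stop treatment (8.5), have no week-24 response visit listed (9.3), and are non-responders if the result is missing (17.2.1). What remains is mainly PD first met at the week-24 assessment.

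**4. Gloss against Appendix 3.** Leave PD aside, assume no new signs or symptoms, and cross: monoclonal protein detectable or not (2), IgM normal or not (2), IgM fall below 25%, 25 to <50%, 50 to <90%, ≥90% (4), extramedullary disease absent at baseline, resolved, reduced or unchanged (4), marrow normal or not (2). That gives 2 × 2 × 4 × 4 × 2 = 128 states.

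- Protein detectable: three cells have no category, namely a 50 to <90% fall with nodes unchanged, and a ≥90% fall with nodes reduced or unchanged. Each covers 2 × 2 states: 3 × 4 = 12.
- Protein undetectable: 64 states, of which CR takes 4 IgM bands × 2 nodal states = 8, leaving 56.
- Total without a category: 12 + 56 = 68. With a fall of at least 25%: 12 + 56 × 3/4 = 54.

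The gloss makes all 54 responders, except at a fall of exactly 25%. The step-down rule given in the fix also makes all 54 responders, leaves no state empty, and changes none of the 128 - 68 = 60 states already classified. Only 2 nodal states × 3 combinations of IgM and marrow = 6 states move into VGPR, all with negative immunofixation. These are counts of table cells, not patient frequencies.

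Outside these patterns, the gloss and Appendix 3 also disagree on a CR with a fall below 25%. Entry asks only for measurable disease "defined as a detectable level of IgM paraprotein", so a low starting IgM is possible.

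**5. Size at the cut-off.** P(X = 23 | 0.60) = 0.8032 - 0.7062 = 0.0970. At true rates of 50% and 55% it is 0.1016 and 0.1229. The plan does not name its interval method; taking Clopper-Pearson, the 90% lower limit is 0.410 at 23/42 and 0.387 at 22/42, on either side of 40%.

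**6. Flare.** IgM 30, then a confirmed 39, then 18 at week 24: (39 - 30)/30 = +30%, which meets both the flare description and the PD threshold. Then (18 - 30)/30 = -40%, which is MR.

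**The case against.** The strongest reply is that the primary endpoint is binary and four sections already say what a response is. On that text a 60% fall with unchanged nodes is a response, and no section says an unclassified patient is a non-responder. This stands. A reader might infer that the empty categories would remove responders, and that losing one would cut power from 80.3% to 70.6% (0.7062, as if 24 were needed). That requires Appendix 3 to override the gloss, unclassified to mean non-responder, and one such loss in every trial; the documents establish none of these.

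The section 9.2.2 requirement, the repeat CT and the marrow taken for response (Appendix 1, notes g and h) do suggest that Appendix 3 is meant to govern. They do not make the gloss disappear.

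It can also be said that *by* is loose drafting, that progression is mostly handled, and that inconclusive progression goes to the TMG or UCL CTC (Appendix 3 note, section 12.5). The first is plausible, but section 17 is what the analyst will follow. The second narrows the gap without closing it. The third covers doubtful progression, not a confirmed rise that meets two definitions.

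Finally, the source cited for Appendix 3 may contain a step-down rule. That cannot be checked from these documents.

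**Conclusion.** The concern holds as an inconsistency in the primary endpoint that should be settled in wording before the analysis. The parts that can change the responder count on the text as it stands are *at* against *by*, and the missing precedence for an observed week-24 result that meets both a response category and PD.

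The empty Appendix 3 categories change the primary count only on the strict reading described above. Otherwise they affect depth of response and best response, and the VGPR rate only when immunofixation is negative but another CR condition is unmet. The gloss is looser in omitting the other conditions, but slightly stricter at a fall of exactly 25%.

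The documents give no frequency for any of these patterns, so no expected bias can be stated. Losing one responder reverses the result only when the more generous count is exactly 23, which has probability 9.7% if the true rate on that count is 60%. A reader might infer an inflated type I error or a faulty sample size; neither is shown, and 42 and 23 are not in error.

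**What to change.** 1. In sections 17.1 and 17.2.1, use *at 24 weeks*, matching sections 1.1, 3.1.1 and 3.2.1 and the missing-data table.
2. State that a patient whose confirmed status at the week-24 assessment is PD is a non-responder.
3. In sections 1.1, 3.2.1, 17.1 and 17.2.1, replace the IgM gloss with *as defined in Appendix 3*, but only together with two additions to Appendix 3, for endpoint classification:
   - A patient who meets a category's IgM minimum but misses another of its conditions takes the next lower category whose IgM minimum and remaining conditions are met. Upper IgM limits do not block this.
   - Undetectable monoclonal IgM does not by itself bar VGPR, PR, MR or SD.

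   Removing the gloss alone would delete the text that now settles these patients. With both additions, responder status in the three patterns stays as the gloss gives it, apart from falls of exactly 25%.
4. Correct the appendix cross-references (editorial).
5. The sponsor should reconcile sections 8.3.3, 8.4.6 and 8.5 with the Appendix 3 PD threshold and state whether an early IgM rise recorded as flare counts as progression for the endpoints. No management rule is proposed here.

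**Cost.** Wording only, with no new data. The step-down is a trial-specific addition to the printed criteria and should be reported as such. *At* may give a slightly lower response rate than *by*; earlier responses are still captured in the best-response analysis of section 17.2.2.

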APPENDIX 4: PROTOCOL VERSION HISTORY

Protocol:		Amendments:		
Version no.	Date	Amendment no.	Protocol Section (no./title)	Summary of main changes from previous version.
1	12/10/18	Initial submission	n/a	n/a
1.1	19/12/18	Response to MHRA grounds of non-acceptance	6.2.1 6.3.3 and throughout 6.3.5	-Clarifying the Bilirubin levels required for trial inclusion -Clarifying that the urine pregnancy test should be highly sensitive test (minimum sensitivity 25 IU/l) -Amending information to state that patients that become pregnant prior to initiating treatment will be withdrawn from the trial
1.2	12/02/19	Response to REC provisional opinion	14.4.3 17.3	-Addition of trigger points for IDMC review of safety data

2.0	010/05/21	Amendment 08	TMG	
 -Update to members -Update to duration of recruitment and total sites - Clarifying the description of measurable disease -Allowing more severe cytopenias, with no lower limit if cytopenia is due to bone marrow involvement and growth factor/transfusion support permitted prior to C1D1.
			6.2.1	
 -BTK inhibitors allowed up until 48 hours prior to C1D1 -Addition of live-attenuated vaccines -Clarifying the exclusion of Hep C positive patients -Allowing a short course of oral prednisolone within 7 days of C1D1 following BTK inhibitor discontinuation -Allowing a subset of patients with a history of colitis -Removal of current participation in any other CTIMP when C1D1 commences
			6.2.2	
 -Addition of pre-registration process to assign a trial number prior to full registration to enable translational samples to be sent to central laboratory
			7.1, 7.2 and throughout	
 -Allowing patients with cytopenias Grade 4 (as per CTCAE v5.0) to receive treatment -Allowing treatment to be moved due to logistical reasons
			8.3	
 -Updated management of irAEs table
			8.4.2	
 -Guidance added for the use of vaccines -Guidance added for the use of growth factor/transfusions
			8.7	
 -Updated MSD out of hours telephone number
			8.10	
 -Addition of remote monitoring and the escalation process for monitoring issues
			14	
 -Addition of the withdrawal of consent process and clarifications made for losses to follow-up
